5.7.1. Criteria for Calculation and Reporting of Area Under the Concentration-time Curve

The minimum requirement for the calculation of AUC will be the inclusion of at least 3 consecutive concentrations above the lower limit of quantification. If there are only 3 consecutive concentrations, at least 1 should follow C_{max} .

For calculation of the partial AUC parameters, if the end interval PK sample is collected slightly earlier than the nominal time, the AUC parameter will be calculated using the end interval sample if the collection is within $\pm 10\%$ of the nominal sampling time.

5.7.2. Criteria for Handling Concentrations Below the Limit of Quantification or Missing Concentrations for Pharmacokinetic Analysis

Serum concentrations below the limit of quantification (BLQ) will be assigned a value of 0 before the first measurable concentration and thereafter BLQ concentrations will be treated as missing. The following rules apply to the specific situations defined below:

- If an entire concentration-time profile is BLQ, it will be excluded from PK analysis.
- Where 2 or more consecutive concentrations are BLQ at the end of a concentration-time curve, the curve will be deemed to have terminated and any further quantifiable concentrations will be set to missing for the calculation of the PK parameters, unless they are considered to be a true characteristic of the profile of the drug.
- If a predose serum concentration is missing on the first day of dosing day (Cycle 1 Day 1), it will be set to 0 by default within Phoenix WinNonlin.

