4.2.7. Handling of Partial and Missing Laboratory Data

Missing laboratory data will not be imputed. However, laboratory values of the form of “< x” (i.e., below the lower limit of quantification) or “> x” (i.e., above the upper limit of quantification) will be imputed as “x” for the purpose of calculation of summary statistics and comparing to normal ranges. These values will still be displayed as “< x” or “> x” in the listings.

4.2.8. Handling of Serum PK Concentrations for Study Treatment that are Below the Lower Limit of Quantification

Serum PK concentrations for Study Treatment that are Below the Lower Limit of Quantification (BLQ) will be handled as follows for descriptive statistics:

- For individual data listings, values that are BLQ (*add actual BLQ for nanrilkefusp alfa and cetuximab in ng/mL here*) will be reported as < LLOQ where LLOQ will be replaced by the actual value for LLOQ for the specific PK assay.
- Values that are BLQ will be set to 0 for the calculation of summary statistics by treatment at each scheduled time point (number of patients in analysis set (N), number of patients with data available (n), arithmetic mean, geometric mean, arithmetic SD, geometric coefficient of variation (%CV), 95% confidence interval (CI), median, min, and max).
- If there are less than 3 quantifiable values in a data series, only the minimum, maximum and n will be presented. The other summary statistics will be denoted as not calculated (NC).

- BLQ results (treated as 0) are in a series of summarized data, geometric mean and CV% will be reported as NC.
- Arithmetic mean or median values that are BLQ presented as 0.
- If a *predose* concentration is missing prior to the first dose of Cycle 1 Day 1, the values will be set to zero.

5. Statistical Methods

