5.7. Pharmacokinetic Analysis

The serum concentrations will be evaluated for nanrilkefusp alfa analyte and may or may not be evaluated for the cetuximab analyte (cetuximab samples will be collected to be analyzed later during the course of the study, if needed). Serum samples will be collected from all patients in the initial safety cohorts and from the first 12 patients in the main study cohort. The actual date and time (24-hour clock time) of each serum sample will be recorded.

The following PK parameters will be determined where possible from the serum concentrations of nanrilkefusp alfa using non-compartmental methods in the validated software program Phoenix WinNonlin (Certara, Version 8.3.5 or higher):

Parameter	Definition
AUC_{last}	area under the concentration-time curve over the last measurable concentration (T_{last}) (Cycle 1 Day 1 only)
$AUC_{(0-4h)}$	area under the concentration-time curve over time 0 to 4 hours postdose (Cycle 1 Day 1 only)
$AUC_{(0-24h)}$	area under the concentration-time curve over time 0 to 24 hours postdose (Cycle 1 Day 1 only)
C_{max}	observed maximum concentration (Cycle 1 Day 1 only)
C_{2h}	observed concentration at 2 hours postdose (Cycle 1 and 3 Days 1)

Parameter	Definition
C_{trough}	observed trough concentration (Cycle 1 Day 2 predose = Cycle 1 Day 1 trough; Cycle 1 Day 9 predose = Cycle 1 Day 8 trough; Cycle 3 Day 1 predose = Cycle 2 Day 9 trough)
T_{max}	time to maximum concentration (Cycle 1 Day 1 only)
T_{last}	time of the last measurable concentration (Cycle 1 Day 1 only)
R_{C2h} , and $R_{C_{trough}}$	Accumulation Ratio of C_{2h} on Cycle 3 Day 1/Cycle 1 Day 1 Accumulation Ratio of C_{trough} on Cycle 2 Day 9/Cycle 1 Day 1

For the Cycle 1 Day 1 profile, the Cycle 1 Day 2 predose concentration will be the 24 hour timepoint.

If cetuximab concentrations are available, C_{trough} will be reported for Cycle 1 (predose concentration on Day 8 and 15) and Cycle 3 (predose concentration on Day 1).

Additional PK parameters may be determined where appropriate.

The units of the PK parameters will be based on the concentration units provided by the bioanalytical laboratory and the dose units used in the study.

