Pharmacokinetic analysis will be carried out where possible using actual dose administered (μg for nanrilkefusp alfa) and actual postdose blood sampling times. If an actual time is missing, the sample concentration result will be treated as missing unless there is scientific justification to include the result using the nominal time.

The parameters C_{max} , C_{trough} , C_{2h} , T_{last} , and T_{max} will be obtained directly from the concentration-time profiles. If C_{max} occurs at more than 1 timepoint, T_{max} will be assigned to the first occurrence of C_{max} .

The area under the concentration-time curve (AUC) parameters will be calculated using the linear trapezoidal rule for increasing concentrations and the logarithmic rule for decreasing concentrations (linear up/log down rule).

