5.7.4. Presentation of Pharmacokinetic Data

A listing of PK blood sample collection times and serum concentrations will be presented for evaluated analyte(s) separately for all patients for the ASaT Population.

PK concentrations will be summarized for the PK Population by analyte, cycle, profile day, treatment, and protocol scheduled times using appropriate summary statistics. See [Section 4.2.8](#) for the handling of serum concentrations that are BLQ and the summary statistics to be presented.

Individual concentrations deemed to be anomalous will be flagged in the listings and excluded from the summary statistics. Individual and summary concentration-time figures will be

presented on both linear and semi-logarithmic scales. PK concentrations by analyte, cycle, profile day, treatment, and nominal time postdose will be displayed for the PK Population using arithmetic mean (+ SD) figures and median figures. Overlaying individual figures and individual figures will be displayed using actual time postdose. For all individual and summary concentration-time figures: Cycle 1 Day 2 predose will be set as the 24 hour postdose concentration for the Cycle 1 Day 1 profile for nanrilkefusp alfa; the Cycle 1 Day 8 predose will be set as the 168 hour postdose concentration for the Cycle 1 Day 1 profile for cetuximab.

A listing of PK parameters will be presented for evaluated analyte(s) separately for all patients in the PK Population.

PK parameters will be summarized for the PK Population by analyte, cycle, profile day, and treatment using the summary statistics: geometric mean, CV% (inter-patient), arithmetic mean, SD, median, minimum, maximum, number of patients with data available (n), and number of patients in analysis set (N), with the exception of T_{max} and T_{last} where only N, n, minimum, median and maximum will be presented. PK parameter summary statistics will be calculated only if there are at least 3 evaluable data ($n \geq 3$) available, otherwise only the N, n, minimum and the maximum are presented and other statistics are shown as not calculated (NC).

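### A Cycle 1 Day 2 predose value below quantification drops out of the Day 1 C_trough summary and of R_Ctrough, but counts as 0 in the concentration table

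*SAP*

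**What the plan says.** - **Parameter derivation (SAP 5.7.2).** BLQ results are 0 "before the first measurable concentration and thereafter BLQ concentrations will be treated as missing". For a profile with no measurable value: "If an entire concentration-time profile is BLQ, it will be excluded from PK analysis".
- **How C_trough arises (SAP 5.7).** C_trough, like C_max and C_2h, "will be obtained directly from the concentration-time profiles". The sampling points are defined as "Cycle 1 Day 2 predose = Cycle 1 Day 1 trough; Cycle 1 Day 9 predose = Cycle 1 Day 8 trough", and the Cycle 3 Day 1 predose sample is the Cycle 2 Day 9 trough. The same section makes the Cycle 1 Day 2 predose sample the 24-hour point of the Day 1 profile. R_Ctrough divides the Cycle 2 Day 9 trough by the Cycle 1 Day 1 trough.
- **Concentration summaries (SAP 4.2.8).** BLQ concentrations "will be handled as follows for descriptive statistics", and the rule is "Values that are BLQ will be set to 0 for the calculation of summary statistics by treatment at each scheduled time point".
- **Presentation (SAP 5.7.4).** The paragraph on concentrations points to 4.2.8 "for the handling of serum concentrations that are BLQ and the summary statistics to be presented". The paragraph on parameters does not point there and has no BLQ rule of its own. It says "PK parameter summary statistics will be calculated only if there are at least 3 evaluable data".

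**The concern.** Treating trailing BLQ points as missing is a device for AUC, where a run of zeros would distort the tail of the curve. A trough is different, because a BLQ trough is itself the result: exposure at that time was too low to measure. Once it is recoded as missing, the patients with the lowest troughs leave the summary and those who remain look better exposed than the group was.

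Two tables will also report different means for one draw, and nothing in the SAP explains why. R_Ctrough loses the same patients through its denominator. Characterising nanrilkefusp alfa PK is a secondary objective in a small subset, so a few lost values can move the summary.

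**Working it through.** **Inputs**
- PK subset: all safety-cohort patients (6 to 12, SAP 2.3) plus the first 12 in the main cohort (SAP 5.7). This gives 6 + 12 = 18 to 12 + 12 = 24, before any replacement of patients not evaluable for DLT.
- LLOQ: not given; SAP 4.2.8 holds a placeholder. The BLQ fraction f is therefore an assumption, shown from 10% to 75%.
- Distribution: log-normal troughs with CV 30%, 60% or 100%, also assumed.
- The plan states no C_trough figure, so there is none to reproduce.

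**Step 1. Trace a BLQ result at each trough, reading 5.7.2 per profile.**
- *Cycle 1 Day 2 predose.* This is the last point of the Day 1 profile. If any earlier Day 1 sample is measurable, the BLQ value follows it and is missing. If none is, the whole profile is excluded. Either way it does not count.
- *Cycle 1 Day 9 predose.* If it opens a Day 9 profile (2 h and 4 h samples follow in Protocol Table 1.1), it precedes the first measurable value and is 0. It is lost if that whole profile is BLQ, or if the sample is attached to the Day 8 dose and the rule runs across days. The SAP calls it the Day 8 trough and does not say which profile holds it.
- *Cycle 3 Day 1 predose.* A 2 h sample follows. If that is measurable, the predose value is 0; if both are BLQ, the profile is excluded.

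So only the Day 1 trough is clearly affected. In R_Ctrough, a BLQ numerator can survive as 0 while a BLQ denominator removes the patient.

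**Step 2. Compare the two tables for the same draw.** With N patients, n of them quantifiable and S the sum of quantifiable values, the C_trough mean is S/n and the 4.2.8 mean is S/N. The ratio is N/n = 1/(1−f), with no distributional assumption. For example, 9 BLQ of 18, or 12 of 24, gives 2.0.

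**Step 3. Compare with the true mean.** With σ² = ln(1+CV²) and z = Φ⁻¹(f):
- BLQ missing: mean / true mean = Φ(σ−z)/(1−f)
- BLQ = 0: mean / true mean = Φ(σ−z)

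Check at f = 50%, CV 30%: σ = √ln(1.09) = 0.294, z = 0, Φ(0.294) = 0.615, and 0.615/0.5 = 1.23.

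| f (assumed) | Missing vs BLQ = 0 | Missing vs true, CV 30 / 60 / 100% | BLQ = 0 vs true, CV 30 / 60 / 100% |
|---|---|---|---|
| 10% | 1.111 | 1.047 / 1.074 / 1.092 | 0.942 / 0.967 / 0.983 |
| 25% | 1.333 | 1.111 / 1.187 / 1.245 | 0.833 / 0.890 / 0.934 |
| 50% | 2.000 | 1.231 / 1.421 / 1.595 | 0.615 / 0.710 / 0.797 |
| 75% | 4.000 | 1.407 / 1.809 / 2.251 | 0.352 / 0.452 / 0.563 |

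Under the missing rule the other location statistics shift too. At f = 50% the geometric mean is 1.264 / 1.556 / 1.943 times its true value and the median 1.219 / 1.454 / 1.753 times.

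**Step 4. Chance that the summary is suppressed.** Fewer than three evaluable values leaves only counts and extremes. At f = 75% the binomial probability is 14% for N = 18 and 4% for N = 24; at f = 90% it is 73% and 56%.

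**Step 5. AUC(0-24h).** Protocol Table 1.1 makes the 12 h sample conditional on logistics. If it was not taken and the 24 h sample is BLQ, usable Day 1 data end at 4 h. SAP 5.7 and 5.7.1 give no extrapolation rule, so AUC(0-24h) has no observed end point in those patients.

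**The case against.** The strongest reply is that the two rules have separate stated scopes: 4.2.8 covers descriptive statistics of concentrations, and 5.7.2 covers parameter derivation. A reader might infer that 5.7.2 breaches the SAP's own BLQ = 0 rule. It does not. What remains is that one sample falls under both rules and gets two values without comment.

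A reader might also infer that every trough is summarised only in patients with measurable drug, so that washout before Cycle 3 is hidden. The documents do not support this. Per profile is the more natural reading: 5.7.2 speaks of whole profiles and of the end of a curve, and 5.7.4 summarises by profile day. On that reading the later troughs are kept as 0 unless their whole profile is BLQ. On any reading, 4.2.8 shows the same draw as 0 in the concentration table and as below LLOQ in the listings.

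The parameter table does show n beside N, so some loss is visible. That helps only in part: samples with no recorded time are also generally treated as missing (SAP 5.7), so n below N cannot be read as a BLQ count.

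Finally, zero is not a neutral substitute. At f = 50% it gives 0.62 to 0.80 times the true mean, makes the geometric mean incalculable, and leaves R_Ctrough undefined when its denominator is 0. This stands, and it shapes the remedy.

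**Conclusion.** The concern holds for the Cycle 1 Day 1 trough and for R_Ctrough. Followed as written, the SAP removes the lowest Day 1 troughs and biases their summary upward whenever any is BLQ. The 1/(1−f) ratio to the 4.2.8 mean is exact wherever both means are reported. The factor of about 1.2 to 1.6 against the true mean assumes log-normal troughs, CV 30% to 100% and f = 50%.

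The actual size cannot be known from the documents, because neither LLOQ nor BLQ rate is given; calling the bias large would go beyond them. For the Cycle 1 Day 9 and Cycle 3 Day 1 predose troughs, the effect depends on whether the rule runs across dosing days or the whole profile is BLQ, and the SAP leaves the first of these open. The reach is modest: a descriptive secondary PK objective in about 18 to 24 patients. ORR, sample size and the futility rule do not use C_trough.

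**What to change.** Amend SAP 5.7.2 and the parameter paragraph of 5.7.4 before database lock:

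1. Limit the treated-as-missing rule to the AUC calculation and state that it is applied per profile.
2. Keep BLQ C_trough and C_2h results in n as values below LLOQ, including when the whole profile is BLQ.
3. Report n (%) BLQ at each trough, with median and range as the lead statistics. With BLQ results ranked lowest, the median is unaffected while fewer than half are BLQ; beyond that it is reported as below LLOQ.
4. If an arithmetic mean is shown with BLQ = 0 as in 4.2.8, note that it is biased downward and that the geometric mean is not calculated.
5. Report R_Ctrough as not calculated when the Cycle 1 Day 1 trough is BLQ, with the number of patients.
6. For AUC(0-24h), report how many patients lack it because the 24 h sample was BLQ, alongside the AUC(0-4h) already planned.

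The cost is a few sentences and a BLQ count in the parameter tables, with no new samples. The price is that geometric means are not available for troughs with BLQ results, which 4.2.8 already accepts for concentrations.

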5.7.3. Treatment of Outliers in Pharmacokinetic Analysis

If a value is considered to be anomalous due to being inconsistent with the expected PK profile, it may be appropriate to exclude the value from the PK analysis. However, the exclusion of any data must have strong justification and will be documented in data review meeting minutes.

Any quantifiable predose concentration value on the first day of dosing (Cycle 1 Day 1) will be considered anomalous and set to missing which Phoenix WinNonlin will apply as 0 by default for the PK analysis.

5.7.4. Presentation of Pharmacokinetic Data

A listing of PK blood sample collection times and serum concentrations will be presented for evaluated analyte(s) separately for all patients for the ASaT Population.

PK concentrations will be summarized for the PK Population by analyte, cycle, profile day, treatment, and protocol scheduled times using appropriate summary statistics. See [Section 4.2.8](#) for the handling of serum concentrations that are BLQ and the summary statistics to be presented.

Individual concentrations deemed to be anomalous will be flagged in the listings and excluded from the summary statistics. Individual and summary concentration-time figures will be

presented on both linear and semi-logarithmic scales. PK concentrations by analyte, cycle, profile day, treatment, and nominal time postdose will be displayed for the PK Population using arithmetic mean (+ SD) figures and median figures. Overlaying individual figures and individual figures will be displayed using actual time postdose. For all individual and summary concentration-time figures: Cycle 1 Day 2 predose will be set as the 24 hour postdose concentration for the Cycle 1 Day 1 profile for nanrilkefusp alfa; the Cycle 1 Day 8 predose will be set as the 168 hour postdose concentration for the Cycle 1 Day 1 profile for cetuximab.

A listing of PK parameters will be presented for evaluated analyte(s) separately for all patients in the PK Population.

PK parameters will be summarized for the PK Population by analyte, cycle, profile day, and treatment using the summary statistics: geometric mean, CV% (inter-patient), arithmetic mean, SD, median, minimum, maximum, number of patients with data available (n), and number of patients in analysis set (N), with the exception of T_{max} and T_{last} where only N, n, minimum, median and maximum will be presented. PK parameter summary statistics will be calculated only if there are at least 3 evaluable data ($n \geq 3$) available, otherwise only the N, n, minimum and the maximum are presented and other statistics are shown as not calculated (NC).

5.8. Immunogenicity Assessments

5.8.1. Anti-Drug Antibodies (ADAs) against nanrilkefusp alfa

Samples for ADAs will be collected to assess nanrilkefusp alfa immunogenicity, correlation with PK, and potential AEs associated with ADAs against nanrilkefusp alfa and for the prediction of nanrilkefusp alfa ADA production, including neutralizing ADAs. The correlation assessments will not be reported.

The presence or absence of anti-drug antibodies, neutralizing ADA's and titer categorizations will be summarized by timepoint and actual nanrilkefusp alfa dose level for the ASaT population.

Immunogenicity data will be listed for the screened population.

5.8.2. ADAs against cetuximab

Samples for cetuximab ADAs will be collected. The decision to analyze the samples to assess cetuximab immunogenicity will be taken at a later date and described separately.

5.9. Biomarkers

Biomarker collection data from eCRF will be listed for screened population. Biomarkers results will be reported separately for the CSR.

6. Changes in the Conduct of the Study or Planned Analysis

The following changes or precisions from protocol specified statistical analyses are made in this SAP.

6.1. SD and iSD derivation

SD and iSD needs to last at least 6 weeks from the start of study treatment and not weeks from the baseline scan as it is mentioned in protocol section 9.3.3.1.

6.2. Duration of Follow-Up

Duration of Follow-Up was added as a reverse Kaplan-Meier analysis on OS to estimate the median follow-up incorporating censoring rules and flipping event/censored events.

6.3. PK parameters

Adjusted PK parameters from those listed in the protocol will be derived. The modified PK parameters documented in section 5.7 include only those that are calculable by non-compartmental analysis based on the adjusted PK sampling timepoints in protocol amendment 1.

7. Appendices

